8.1.5. Other analysis

- (1) Case distribution: Different data sets in each group, case distribution in each Site, comparison of total drop-off rate, detailed list of termination reasons, and descriptive analysis.
- (2) Compliance analysis: Compare whether the two groups of patients take the test drugs on time and in quantity, whether they take the drugs and foods prohibited in the Protocol, and conduct the same descriptive analysis as well as χ^2 test or Fisher test for analysis.
- (3) The incidence of drug withdrawal or drug change due to adverse reactions in the clinical trial shall be analyzed with χ^2 test or Fisher test. The efficacy in the long-term follow-up after the trial is evaluated by descriptive analysis and χ^2 test or Fisher test.

8.1.6. Safety analysis

Safety analysis mainly adopts safety set. All adverse events are coded by MedDRA 20.0 to describe the total number and incidence of adverse events (including serious adverse events), and the

frequency table is used to describe the frequency, severity of each adverse event and its relationship with the treatment. Adverse events relevant (related, probably related, and possibly related) to this research treatment are described and listed separately. Other safety indicators will also be described and summarized. The laboratory changes with clinical significance will be counted as AE.

9. Statistical analysis results

9.1. Research overview

Table 1. Distribution of subjects at each site (All enrolled subjects)

Research Site	Group	No. of subjects enrolled	No. of subjects drop-out	Drop-out rate	No. of subjects eliminated	Elimination rate	No. of subjects completed
Site 1	Experimental group						
	Control group						
	Total						
Site 2	Experimental group						
	Control group						
	Total						
...							
Total	Experimental group						
	Control group						
	Total						

Note: 1. The Site name is not displayed in following table, only the site number. Same below. 2. No. of subjects completed = No. of subjects enrolled - No. of subjects drop-out. Elimination refers to subjects who complete the trial, but were not included in the PPS. Subjects who withdrew due to the endpoint event were considered to have completed the trial. 3. Drop-out rate = No. of subjects drop-out / No. of subjects enrolled; Elimination rate = No. of subjects eliminated / No. of subjects enrolled.

Table 2. Distribution of subjects at each site

Site	PPS			FAS			SS		
	Experimental group	Control group	Total	Experimental group	Control group	Total	Experimental group	Control group	Total
Site 1									
Site 2									
Total									

Table 3. Trial completion and distribution of analysis data set (All enrolled subjects)

Items	Indicator	Experimental group	Control group	Total
No. of subjects enrolled	Yes			
	No			
Complete 1 week follow-up	Yes			
	No			
Complete 4 week follow-up	Yes			
	No			
Complete 8 week follow-up	Yes			
	No			
Complete 16 week follow-up	Yes			
	No			
Complete 24 week follow-up	Yes			
	No			
Complete 32 week follow-up	Yes			
	No			
Complete 40 week follow-up	Yes			
	No			
Complete 52 week follow-up	Yes			
	No			
Trial completion	Yes			

Items	Indicator	Experimental group	Control group	Total
	No			
Treatment discontinuation reason	Subject voluntarily withdrew prematurely			
	Decision by the investigator			
	Poor compliance that decided by the investigator			
	Meet the exclusion criteria, or did not meet the inclusion criteria			
	Refusal to continue trial participation			
	Lack of efficacy			
	Adverse events			
	Lost to follow-up			
	Death			
	Other			
FAS				
PPS				
SS				

Note: Follow-up time (years) = (last visit date - random date + 1) / 365.25. Complete 1 week follow-up: follow-up duration \geq 1 week, and so on.

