5.2.2 Treatment of relapses

If the disease is complicated with infection in the relapse for the pediatric patients, anti-infection treatment can be given first. After infection control, if the disease still shows relapse, the prednisone dose shall be restored to 1.0-1.5 mg/kg per day, with a maximum dose ≤ 60mg; If there is no infection at the time of relapse in the pediatric patients, the prednisone dose should be restored to 1.0-1.5 mg/kg per day directly, with a maximum dose ≤ 60mg. 5-7 days after the urine protein turns into negative results, the prednisone dose is reduced by 1.0-1.5 mg/kg every other day or 0.5-0.75mg/kg per day × 4 weeks. Then the dose is reduced as per the above steroid reduction method, while the dose of MMF or FK506 remains unchanged.

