7.2 Efficacy evaluation

7.2.1 Primary observation outcomes: 1-year relapse-free survival

7.2.2 Secondary observation outcomes:

- (1) Frequency of relapses; the time of the first relapse after enrollment; relapse-free **survival** in the first six months after enrollment;
- (2) Renal function: Serum creatinine and glomerular filtration rate (eGFR, see Appendix 1 for the calculation method)
- (3) Cumulative steroid dosage: The total amount of steroids taken during this research and the total amount of steroids in the first half of the year
- (4) Others: Blood pressure (see Appendix 2 for details), height, weight, blood lipid, hemoglobin, blood albumin, urinary protein/creatinine (morning urine), etc.
- (5) Adverse reaction
- (6) 24hr urinary protein quantification (applicable to subjects > 3 years old)

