4.1. Design overview

This trial is a prospective, randomized, multicenter, open-label, parallel-arm clinical study, using the Logrank method to compare the difference of 1-year relapse free survival between the two groups. Enrollment was completed by 12 sites using competitive enrollment. The whole observation period is 1 year for this trial. Eligible patients who sign the informed consent form will be randomly divided into FK506 Group or MMF Group at the ratio of 1:1. Both groups follow the "clinical trial flow chart" in operation.

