4.5.5. Drop-out and treatment

4.5.5.1 Definition of drop-out

All patients who have completed the Informed Consent Form and screened to be enrolled in the trial have the right to withdraw at any time. Whenever and for whatever reason, subjects who fail to complete the observation period specified in the Protocol are considered as drop-out cases, including the following situations:

- The subject has serious adverse events and the clinician believes that he/she should withdraw from the clinical trial;
- The subject shows aggravated condition or has other symptoms affecting the trial observation during the trial, and the clinician believes that he/she should withdraw from the clinical trial;
- Important deviations occur in the implementation of clinical trial protocol, such as poor compliance, which would cause difficulty in evaluating the drug effect;
- The subject is unwilling to continue the clinical trial and asks to withdraw from the clinical trial, or loss of follow-up has occurred although no request to withdraw from the trial is proposed.

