6.2. Efficacy evaluation

6.2.1. Primary observation outcomes: 1-year relapse-free survival

6.2.2. Secondary observation outcomes:

- (1) Frequency of relapses; the time of the first relapse after enrollment; relapse-free survival in the first six months after enrollment;
- (2) Renal function: Serum creatinine and glomerular filtration rate (eGFR, see Appendix 1 for the calculation method)
- (3) Cumulative steroid dosage: The total amount of steroids taken during this research and the total amount of steroids in the first half of the year
- (4) Others: Blood pressure (see Appendix 2 for details), height, weight, blood lipid, hemoglobin, blood albumin, urinary protein/creatinine (morning urine), etc.
- (5) Adverse reaction
- (6) 24hr urinary protein quantification (applicable to subjects > 3 years old)

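### SAP Table 1 counts a child who withdraws at relapse as a completer, against the plan's own drop-out definition, so the drop-out rate and its between-arm comparison omit relapse-related leavers

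*SAP*

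**What the plan says.** **Two rules for the same child.** SAP section 9.1, Table 1 note 2, gives the identity "No. of subjects completed = No. of subjects enrolled - No. of subjects drop-out" and adds "Subjects who withdrew due to the endpoint event were considered to have completed the trial". Taken together, a child who withdraws because of relapse is a completer and cannot be a drop-out.

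SAP 4.5.5.1, in the same words as protocol 4.5.1, says: "Whenever and for whatever reason, subjects who fail to complete the observation period specified in the Protocol are considered as drop-out cases". SAP 4.1 fixes that period: "The whole observation period is 1 year for this trial".

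**What is planned after a relapse.** Protocol 5.2.2 treats the relapse with prednisone and ends: "Then the dose is reduced as per the above steroid reduction method, while the dose of MMF or FK506 remains unchanged". Relapse is not among the mandatory withdrawal conditions (protocol 4.4, SAP 4.5.4).

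**Outcomes that depend on follow-up after the first relapse.** SAP 6.2.2 lists "Frequency of relapses; the time of the first relapse after enrollment; relapse-free survival in the first six months after enrollment". Protocol 7.2.2 defines cumulative steroid dosage as "The total amount of steroids taken during this research and the total amount of steroids in the first half of the year". SAP Tables 28 and 29 show the steroid dose as raw totals, and relapse frequency has no results table. Neither outcome has a rule for unequal follow-up. The missing-data convention in SAP section 8 is justified only by reference to survival data.

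**Where the drop-out count is used.** SAP 8.1.5 plans a comparison of the total drop-off rate and a list of termination reasons.

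**The concern.** A child who relapses, leaves and is not seen again before visit 9 is a completer under the table note and a drop-out under the definition. The result in Table 1, and the comparison of drop-off between arms, depends on which rule the programmer follows. If it is the note, the omitted children are those who left after the primary event. The plan expects more such events on MMF, so the omission would be unequal unless the leaving share differed enough between arms to offset it.

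Such exits are not excluded. Protocol 4.5.1 lets the clinician withdraw a child whose condition worsens, protocol 4.5.2 mentions withdrawal for ineffective treatment, and Table 3 carries a lack-of-efficacy reason. Relapse frequency and total steroid dose need the whole year. If a child leaves at relapse and recording stops, later relapses and the steroid course for that relapse go unrecorded, and no analysis rule allows for the shorter follow-up.

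**Working it through.** **Inputs.** 1-year relapse-free survival S = 0.56 (MMF) and 0.70 (FK506); 114 + 115 = 229 evaluable; 15% loss; 270 randomised, 135 per arm; accrual 2 years, total 3 years (protocol 3.3.2 and Appendix 4, SAP 4.2.2). The share q of relapsing children who leave is not in the documents. It is an assumption, shown over a range and taken as equal in both arms.

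**Step 1: reproduce the plan's figures.** With exponential relapse times, h = -ln S = 0.580 (MMF) and 0.357 (FK506) per year.
- Hazard ratio: 0.357/0.580 = 0.615 (stated 0.6151).
- Events: the chance of an event is 1 - [exp(-h) - exp(-3h)]/(2h). This gives 76.2 + 57.4, about 133.7 (stated 133.8).
- Power from a Lakatos-type calculation: 0.800 (stated 0.8009).
- Inflation: 229/0.85 = 269.4, rounded up to 270 (stated 270).

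The planned rates can therefore be used for what follows.

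**Step 2: children missing from the drop-out count.** The 1-year relapse risk is 1 - S = 0.44 and 0.30. If a share q leaves at first relapse, the definition in 4.5.5.1 counts q x 0.44 and q x 0.30 of each arm as drop-outs; the note counts none of them. Per 135 children:

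| q | MMF omitted | FK506 omitted |
|---|---|---|
| 0% | 0 | 0 |
| 10% | 5.9 (4.4%) | 4.1 (3.0%) |
| 25% | 14.8 (11.0%) | 10.1 (7.5%) |
| 50% | 29.7 (22.0%) | 20.3 (15.0%) |
| 100% | 59.4 (44.0%) | 40.5 (30.0%) |

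**Step 3: possible effect on full-year outcomes, if leavers' data also stop.** Here a child leaves with probability q at each relapse, and the relapse rate is constant. Observed relapses per child are (1 - exp(-hq))/q, against h with full follow-up.

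| q | MMF | FK506 | Difference | Share lost, MMF v FK506 |
|---|---|---|---|---|
| 0% | 0.580 | 0.357 | 0.223 | 0 v 0 |
| 10% | 0.563 | 0.350 | 0.213 | 2.8% v 1.8% |
| 25% | 0.540 | 0.341 | 0.199 | 6.9% v 4.3% |
| 100% | 0.440 | 0.300 | 0.140 | 24.1% v 15.9% |

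At q = 100%, person-time per child is (1 - S)/h = 0.44/0.580 = 0.759 and 0.30/0.357 = 0.841 years, so 24.1% and 15.9% of follow-up is lost. I give no figure for the steroid total. It would need body weight, time to remission, and whether a cut-off total is analysed or set to missing, none of which the documents state.

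**Step 4: analysis sets.** SAP 8.1.3 counts a relapse within the year as the event, so a later exit does not change time to first relapse. The wording on elimination needs care, however. Note 2 describes eliminated subjects as completers outside the PPS. SAP 7.1 requires completion of the treatment plan for the PPS, and it drops eliminated cases from the FAS while keeping drop-off cases. SAP 4.5.3 also eliminates those who do not complete planned follow-up. Read literally, a relapse-leaver could be a completer, outside the PPS, hence eliminated, hence outside the FAS, and the event would go too.

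**The case against.** The strongest reply is that the note is only a label in a disposition table. It tells no child to leave and no site to stop recording. Protocol 5.2.2 plans for treatment to continue, and protocol 4.5.2 asks investigators to pursue leavers and complete what evaluations they can. For a primary outcome of time to first relapse, treating a child who reached the endpoint as complete is coherent. All of this stands, and it rules out several stronger readings that a reader might infer:

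- *That the note cuts short relapse counts and steroid totals.* It does not. Relabelling a child changes no count or total. The loss in Step 3 needs children to leave and their data to stop, at a share that the documents do not give.
- *That early leaving is hidden altogether.* Table 3 shows follow-up reached at each visit by arm, calculated from the last visit date, and the discontinuation reasons. Tables 28 and 29 show the number missing. Early exits would be partly visible there.
- *That these leavers use up the 15% loss allowance.* That allowance inflates the log-rank sample size, and a child who leaves at relapse has already had the primary event.
- *That completer status brings PPS membership.* The note itself provides for completers outside the PPS.

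What the reply does not remove is the contradiction between the note and the definition, or its direct effect on the Table 1 drop-out rate and the comparison in SAP 8.1.5.

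**Conclusion.** The contradiction is real and should be resolved. Applied as written, note 2 understates drop-out by q x 44% (MMF) and q x 30% (FK506) at the planned rates: about 6 v 4 of 135 children at q = 10% and about 15 v 10 at q = 25%. At q = 0 there is no effect. The direction, with more omitted on MMF, assumes a similar q in both arms.

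A consequence for relapse frequency and steroid dose is possible but conditional. These outcomes can be cut short, more in the arm with more relapse exits, if children leave and collection stops. The primary time-to-first-relapse analysis is unaffected as long as these children stay in the FAS, which the elimination wording does not make certain.

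**What to change.** 1. **Reconcile note 2 with SAP 4.5.5.1.** Report, by arm, those who reached the endpoint separately from those who completed 1-year observation. Count a child who leaves before visit 9 after a relapse as a drop-out with reason relapse.
2. **State the data-collection rule.** After a relapse, relapse dates, steroid dose and scheduled outcomes continue to be collected to Day 364. This concerns data only and leaves the clinical withdrawal rules as they are.
3. **Add a rule for follow-up time.** For example, analyse relapse frequency with a count model that has a log follow-up offset, and steroid dose per unit of time. Show the number who left after relapse beside Tables 28 and 29.
4. **Protect the analysis sets.** Do not remove relapse-leavers from the PPS because of the relabelling, since that would select on the outcome. With q = 50%, PPS relapse would become 22/78 = 28% v 15/85 = 18%, a gap of about 10.6 points instead of the planned 14. Reconcile SAP 4.5.3, SAP 7.1 and note 2 so that relapse events stay in the FAS.

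The cost is SAP wording, a protocol sentence on data collection, a reason code and the specification of two secondary analyses. The visits are already scheduled. The downside is that the reported drop-out rate becomes less favourable.

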9.2. Demographic characteristics (FAS)

Table 4. Baseline demographics

Items	Indicator	Experimental group	Control group	Total
Age (years)	N (Missing)			
	Mean (SD)			
	Median			
	Q1, Q3			
	Min, Max			
	Statistics			
	P-value			
Gender	male n (%)			

Items	Indicator	Experimental group	Control group	Total
	Female n (%)			
	Total (Missing)			
	Statistics			
	P-value			
Ethnicity	Han n (%)			
	Others n (%)			
	Total (Missing)			
	Statistics			
	P-value			
Source of disease	Outpatient n (%)			
	Ward n (%)			
	Total (Missing)			
	Statistics			
	P-value			

Table 5. Baseline vital signs

Items	Indicator	Experimental group	Control group	Total
Height (cm)	N (Missing)			
	Mean (SD)			
	Median			
	Q1, Q3			
	Min, Max			
	Statistics			
	P-value			
Weight (kg)	N (Missing)			
	Mean (SD)			
	Median			
	Q1, Q3			

Items	Indicator	Experimental group	Control group	Total
BMI (kg/m ²)	Min, Max Statistics P-value N (Missing) Mean (SD) Median Q1, Q3 Min, Max Statistics P-value			
Temperature (°C)	N (Missing) Mean (SD) Median Q1, Q3 Min, Max Statistics P-value			
Systolic blood pressure (mmHg)	N (Missing) Mean (SD) Median Q1, Q3 Min, Max Statistics P-value			
Diastolic blood pressure (mmHg)	N (Missing) Mean (SD) Median Q1, Q3			

Items	Indicator	Experimental group	Control group	Total
Heart rate (times/min)	Min, Max			
	Statistics			
	P-value			
	N (Missing)			
	Mean (SD)			
	Median			
	Q1, Q3			
	Min, Max			
	Statistics			
	P-value			
Respiratory rate (times/minute)	N (Missing)			
	Mean (SD)			
	Median			
	Q1, Q3			
	Min, Max			
	Statistics			
	P-value			

Table 6. Family history and personal history

Items	Indicator	Experimental group	Control group	Total
Family history	No n (%)			
	Yes n (%)			
	Total (Missing)			
	Statistics			
	P-value			
History of drug allergy	No n (%)			
	Yes n (%)			
	Total (Missing)			

Items	Indicator	Experimental group	Control group	Total
History of surgery	Statistics			
	P-value			
	No n (%)			
	Yes n (%)			
	Total (Missing)			
History of pet ownership	Statistics			
	P-value			
	No n (%)			
	Yes n (%)			
	Total (Missing)			
Number of gestation	Statistics			
	P-value			
	N (Missing)			
	Mean (SD)			
	Median			
	Q1, Q3			
	Min, Max			
Number of parturition	Statistics			
	P-value			
	N (Missing)			
	Mean (SD)			
	Median			
	Q1, Q3			
	Min, Max			
Birth weight (kg)	Statistics			
	P-value			
	N (Missing)			
	Mean (SD)			

Items	Indicator	Experimental group	Control group	Total
History of dystocia	Median			
	Q1, Q3			
	Min, Max			
	Statistics			
	P-value			
	No n (%)			
	Yes n (%)			
	Total (Missing)			
	Statistics			
	P-value			
Feeding	Mixed feeding n (%)			
	Single feeding n (%)			
	Total (Missing)			
	Statistics			
	P-value			
Partial eclipse	No n (%)			
	Yes n (%)			
	Total (Missing)			
	Statistics			
	P-value			
History of growth and development	Normal n (%)			
	Abnormal n (%)			
	Total (Missing)			
	Statistics			
	P-value			
Vaccination history	No n (%)			
	Yes n (%)			
	Total (Missing)			

Items	Indicator	Experimental group	Control group	Total
	Statistics			
	P-value			

Table 7. History of other diseases, concomitant medications and nephrotic syndrome

Items	Indicator	Experimental group	Control group	Total
History of other diseases and concomitant medications	No n (%)			
	Yes n (%)			
	Total (Missing)			
	Statistics			
	P-value			
History of nephrotic syndrome (years)	N (Missing)			
	Mean (SD)			
	Median			
	Q1, Q3			
	Min, Max			
	Statistics			
	P-value			
History of nephrotic syndrome (Number of relapses in the past 1 year)	N (Missing)			
	Mean (SD)			
	Median			
	Q1, Q3			
	Min, Max			
	Statistics			
	P-value			
History of nephrotic syndrome (Number of relapses in the past 6 months)	N (Missing)			
	Mean (SD)			
	Median			
	Q1, Q3			

Items	Indicator	Experimental group	Control group	Total
	Min, Max			
	Statistics			
	P-value			

Note: History of other diseases and concomitant medications: history of diseases other than the nephrotic syndrome, such as pneumonia, cardiovascular, diabetes, purpura and enuresis, etc.

Table 8. Visual palpation of physical examination Items

Items	Indicator	Experimental group	Control group	Total
Heart	Normal n (%)			
	Abnormal but not clinically significant n (%)			
	Abnormal and clinically significant n (%)			
	Not tested n (%)			
	Total (Missing)			
	Statistics			
	P-value			
Superficial lymph node	Normal n (%)			
	Abnormal but not clinically significant n (%)			
	Abnormal and clinically significant n (%)			
	Not tested n (%)			
	Total (Missing)			
	Statistics			
	P-value			
Skin and sclera	Normal n (%)			
	Abnormal but not clinically significant n (%)			
	Abnormal and clinically significant n (%)			
	Not tested n (%)			
	Total (Missing)			
	Statistics			
	P-value			

Thyroid gland	Normal n (%)
	Abnormal but not clinically significant n (%)
	Abnormal and clinically significant n (%)
	Not tested n (%)
	Total (Missing)
	Statistics
	P-value
	Normal n (%)
	Abnormal but not clinically significant n (%)
	Abnormal and clinically significant n (%)
Limbs and spine	Not tested n (%)
	Total (Missing)
	Statistics
	P-value
	Normal n (%)
	Abnormal but not clinically significant n (%)
	Abnormal and clinically significant n (%)
	Not tested n (%)
	Total (Missing)
	Statistics
Lung, abdomen and back	P-value
	Normal n (%)
	Abnormal but not clinically significant n (%)
	Abnormal and clinically significant n (%)
	Not tested n (%)
	Total (Missing)
	Statistics
	P-value
	Normal n (%)
	Abnormal but not clinically significant n (%)
Nervous system	Abnormal and clinically significant n (%)
	Not tested n (%)
	Total (Missing)
	Statistics
	P-value
	Normal n (%)
	Abnormal but not clinically significant n (%)
	Abnormal and clinically significant n (%)
	Not tested n (%)
	Total (Missing)
Other	Statistics
	P-value
	Normal n (%)

Abnormal but not clinically significant n (%)
 Abnormal and clinically significant n (%)
 Not tested n (%)
 Total (Missing)
 Statistics
 P-value

Table 9. Diagnostic consultation of physical examination Items

Items	Indicator	Experimental group	Control group	Total
Defecation	Normal n (%) Abnormal but not clinically significant n (%) Abnormal and clinically significant n (%) Not tested n (%) Total (Missing) Statistics P-value			
Fever/dizziness/vertigo	Normal n (%) Abnormal but not clinically significant n (%) Abnormal and clinically significant n (%) Not tested n (%) Total (Missing) Statistics P-value			
Dry mouth and eyes	Normal n (%) Abnormal but not clinically significant n (%) Abnormal and clinically significant n (%) Not tested n (%) Total (Missing) Statistics P-value			

	P-value
Gastrointestinal digestion	Normal n (%)
	Abnormal but not clinically significant n (%)
	Abnormal and clinically significant n (%)
	Not tested n (%)
	Total (Missing)
	Statistics
	P-value
Myalgia/muscle weakness	Normal n (%)
	Abnormal but not clinically significant n (%)
	Abnormal and clinically significant n (%)
	Not tested n (%)
	Total (Missing)
	Statistics
	P-value
Arthralgia/arthritis	Normal n (%)
	Abnormal but not clinically significant n (%)
	Abnormal and clinically significant n (%)
	Not tested n (%)
	Total (Missing)
	Statistics
	P-value
Dry/itchy skin	Normal n (%)
	Abnormal but not clinically significant n (%)
	Abnormal and clinically significant n (%)
	Not tested n (%)
	Total (Missing)
	Statistics
	P-value

Other	Normal n (%)
	Abnormal but not clinically significant n (%)
	Abnormal and clinically significant n (%)
	Not tested n (%)
	Total (Missing)
	Statistics
	P-value

